7.1.1.4 Subject Visit Schedule Summary Post-baseline

Following the Baseline Visit (Visit 2), subjects will proceed through the study in 1 of 3 ways.

1. Double-blind Acute Phase → Open-label Acute Phase → Double-blind Maintenance Phase.

Visits completed post-Baseline Visit (Visit 2) are as follows: Visit 3, Visit 3.1, Visit 3.2, Visit 4, Visit 4.1, Visit 4.2, Visit 5, Visit 5.1, Visit 5.2, and Visit 6.

Note that Visit 3.1 and/or Visit 3.2 may not be completed in the case that a subject enters into the Open-label Acute Phase without completing the Double-blind Acute Phase. See Section [7.1.3](#) for the criteria for subject eligibility to enter the Open-label Acute Phase.

2. Double-blind Acute Phase → Double-blind Maintenance Phase.

Visits completed post-Baseline Visit (Visit 2) are as follows: Visit 3, Visit 3.1, Visit 3.2, Visit 5, Visit 5.1, Visit 5.2, and Visit 6.

3. Double-blind Maintenance Phase only.

Visits completed post-Baseline Visit (Visit 2) are as follows: Visit 5, Visit 5.1, Visit 5.2, and Visit 6.

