7.1.2.3 Double-blind Acute Phase Week 8/Withdrawal (Visit 3.2)

The Double-blind Acute Phase Withdrawal Visit may occur at any time the subject discontinues participation in the Double-blind Acute Phase, or at completion of the study at Week 8 of the Double-blind Acute Phase. No additional Baseline Visit is required for subjects continuing into the Open-label Acute Phase or the Double-blind Maintenance Phase from this visit.

Subjects with a clinical response ie, partial UC-DAI ≤ 1 (with rectal bleeding=0 **and** stool frequency ≤ 1 **and** PGA=0) will be weighed and re-randomized into the Double-blind Maintenance Phase for treatment with low- or high-dose MMX mesalamine/mesalazine stratified by weight group based on current weight. Please see Section [6.2.3](#) for weight-stratified randomization groups. Subjects without a clinical response may continue into the Open-label Acute Phase and receive MMX mesalamine/mesalazine at the high dose for their weight group, based on their weight at Visit 3.2 (Week 8/Withdrawal of the Double-blind Acute Phase).

Collection of stool samples for all assessments must occur before administration of any bowel preparations for endoscopy if samples are collected on the same day as bowel preparation administration.

Endoscopy (flexible sigmoidoscopy or colonoscopy) should be performed at Visit 3.2 for subjects who are not entering into the Open-label Acute Phase. If performed, endoscopic video or photographs will be collected and sent to the study's central endoscopy reader for evaluation of mucosal healing. Please see a description of criteria used for endoscopic scoring in [Appendix 2](#). If endoscopy is not performed at Visit 3.2 and the subject is otherwise eligible, the subject may remain in the study.

Subjects and/or caregivers will have collected UC-DAI symptoms (rectal bleeding and stool frequency) via e-diary once a day before bedtime for 5 days prior to each study visit in the Double-blind Acute Phase. The average stool frequency and rectal bleeding scores will be calculated and be made available to the investigator through a report from the e-diary provider. The average stool frequency and rectal bleeding scores will be added to the PGA score determined by the investigator to calculate the partial UC-DAI. Please see a description of the PGA in Section [7.2.1.1](#) and the UC-DAI in Sections [7.2.1.1](#) and [7.2.1.2](#).

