7.1.3 Open-label Acute Phase

Subjects may enter the Open-label Acute Phase after completion of the Double-blind Acute Phase if they do not meet the requirements for entry into the Double-blind Maintenance Phase ie, they do not achieve a clinical response defined as a partial UC-DAI ≤ 1 (with rectal bleeding=0 *and* stool frequency ≤ 1 *and* PGA=0). This phase is intended to allow those subjects without clinical response in the Double-blind Acute Phase an additional 8 weeks to achieve clinical response at the high dose for their weight group. The subject's weight at Visit 3.2 (Week 8/Withdrawal of the Double-blind Acute Phase) will be used to determine the high dose assigned to the subject in the Open-label Acute Phase.

Subjects are also eligible for the Open-label Acute Phase provided they have participated in the Double-blind Acute Phase for a minimum of 2 weeks and, in the investigator's opinion, have not benefited from treatment in the Double-blind Acute Phase. In addition, they should not have experienced a possibly or probably related severe adverse event (AE) or a serious AE (SAE). Due to the delay in onset of action of 5-ASA preparations, investigators should make subjects/caregivers aware that they may not benefit from the investigational product within the first 2 weeks. Subjects who withdraw before Visit 3 will not be eligible for the Open-label Acute Phase.

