7.2.1.2 Modified Full UC-DAI Score

The full UC-DAI is widely used to assess treatment efficacy in subjects with mild to moderate UC (Schroeder et al. 1987; Sutherland et al. 1987). It consists of 4 individual parameters: stool frequency, rectal bleeding, endoscopy score (mucosal appearance), and PGA. For the purpose of this study, the standard UC-DAI scale has been modified so that an endoscopy score of mild disease does not include friability; instead, friability will be scored as 2: moderate disease.

Please see a description of stool frequency, rectal bleeding and PGA in Section [7.2.1.1](#).

All 4 parameters will be assessed individually on a scale from 0-3; the maximum total modified full UC-DAI score is 12.0. The modified full UC-DAI score will be calculated at Baseline (Visit 2), Week 8 of the Double-blind Acute Phase (Withdrawal) for subjects not entering into the Open-label Acute Phase, Week 8 of the Open-label Acute Phase (Withdrawal) for subjects who have not had endoscopy at the end of the Double-blind Acute Phase, and Week 26 of the Double-blind Maintenance Phase (Withdrawal) visits. The total score will be calculated by summing the individual scores for the 4 parameters (endoscopy score will be based on the central reader's score). The site is not required to calculate the full UC-DAI; this will be calculated centrally using e-diary and eCRF data.

For determination of the modified full UC-DAI, the average of the symptom scores of the last available 3 days within the 5-day period immediately prior to study visits where endoscopic data are available, will be used. No symptom data older than 5 days prior to the study visit will be used. Data collected on days when bowel preparations have been administered or when endoscopy has been performed will be excluded.

An endoscopy must be performed and mucosal appearance scored within 21 days prior to the Screening Visit (Visit 1), during the Screening period or at the Baseline Visit (Visit 2) depending on the subject's UC history and phase of the study into which they are entering. All efforts should be made to perform endoscopy at Week 8 of the Double-blind Acute Phase (or Week 8 of the Open-label Acute Phase, as applicable), Week 26 of the Double-blind Maintenance Phase, or the subject's withdrawal if different from these visits.

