5.8 Analysis of Efficacy

All efficacy analyses will be based on the Safety Analysis Set specific to the study phase. Baseline is defined as the last observation prior to first dose of investigational product in the study. The Double-blind Acute Phase Week 8/Withdrawal visit (Visit 3.2) is treated as the Open-label Acute Phase Week 0 for subjects continuing into the Open-label Acute Phase from this visit. The Double-blind Acute Phase Week 8/Withdrawal visit (Visit 3.2) is treated as the Double-blind Maintenance Phase Week 0 for subjects continuing into the Double-blind Maintenance Phase from this visit. The Open-label Acute Phase Week 8/Withdrawal visit (Visit 4.2) is treated as the Double-blind Maintenance Phase Week 0 for subjects continuing into the Double-blind Maintenance Phase from this visit. For subjects who enter the Double-blind Maintenance Phase directly, the Baseline Visit (Visit 2) is treated as the Double-blind Maintenance Phase Week 0.

The final on treatment assessment (FoTA) for the Double-blind Acute phase is defined as data from the Double-blind Acute phase Week 8, or early withdrawal visit if subject withdrew prior to Week 8. The FoTA for the Open-label Acute phase is defined as data from the Open-label Acute phase Week 8, or early withdrawal visit if subject withdrew prior to Week 8. The FoTA for the Double-blind Maintenance phase is defined as data from the Double-blind Maintenance phase Week 26, or early withdrawal visit if subject withdrew prior to Week 26.

Details of the derivation of the composite endpoints (partial and full UC-DAI scores) are included in Section 8.2.

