5.8.2.1 Double-blind Acute Phase

- The proportion of subjects with a clinical and endoscopic response at Week 8, defined as UC-DAI ≤ 2 with rectal bleeding=0 and stool frequency ≤ 1 and PGA=0, and with mucosal healing (endoscopy score ≤ 1) based on central reading. In addition, there must be at least a 1-point reduction in endoscopy score from baseline. This endpoint will be compared between treatment arms using a continuity corrected chi-squared test. If any of the expected cell counts are very low (i.e., less than 5), then Fisher's Exact Test will be used as an alternative analysis method. Subjects with missing data at Week 8 will be assumed not to have had a clinical response. Subjects who completed week 8 but who did not have central reading endoscopies at both baseline and week 8 will be excluded.
- The proportion of subjects with a clinical and endoscopic response at Week 8, defined as UC-DAI ≤ 2 with rectal bleeding=0 and stool frequency ≤ 1 and PGA=0, and with mucosal healing (endoscopy score ≤ 1) based on local reading. In addition, there must be at least a 1-point reduction in endoscopy score from baseline. This endpoint will be compared between treatment arms using a continuity corrected chi-squared test. If any of the expected cell counts are very low (i.e., less than 5), then Fisher's Exact Test will be used as an alternative analysis method. Subjects with missing data at Week 8 will be assumed to be treatment failures. Subjects with missing data at Week 8 will be assumed not to have had a clinical response. Subjects who completed week 8 but who did not have local reading endoscopies at both baseline and week 8 will be excluded.
- The change in the DUCS score from baseline to Week 8 of the Double-blind Acute Phase. This endpoint will be compared between treatment arms using an analysis of covariance (ANCOVA), including treatment arm as a factor and the baseline DUCS score as a covariate in the model.
- The percentage of subjects with an improvement (change of ≥ 20 points) in PUCAI score from baseline to Week 8 of the Double-blind Acute Phase. This endpoint will be compared between treatment arms using a continuity corrected chi-squared test. If any of the expected cell counts are very low (i.e., less than 5), then Fisher's Exact Test will be used as an alternative analysis method. Subjects with missing data at Week 8 will be assumed not to have had a clinical response.

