Abbreviations: DUCS=Daily Ulcerative Colitis Scale for children and caregivers; eCRF=electronic case report form; e-diary=electronic diary; IRT= interactive response technology; PGA=Physician's Global Assessment; PUCAI=Pediatric Ulcerative Colitis Activity Index; UC-DAI=Ulcerative Colitis Disease Activity Index.

^a Approximately 4 to 7 days prior to the Baseline Visit (Visit 2) and prior to each subsequent visit (Visits 3, 3.1, and 3.2), it is recommended that site staff telephone the subject or the subject's caregiver to remind them to enter UC-DAI symptoms (rectal bleeding and stool frequency) into the e-diary every night, even if the subject has no symptoms.

^b Subjects may enter into the Open-label Acute Phase beginning at Visit 3 (after a minimum of 2 weeks double-blind treatment) and at any time until the end of the Double-blind Acute Phase provided all criteria have been met.

^c Subjects will continue into the Open-label Acute Phase if they have not met the criteria to enter the Double-blind Maintenance Phase and are eligible to continue into the Open-label Acute Phase.

^d Subjects will continue into the Double-blind Maintenance Phase if partial UC-DAI ≤ 1 (with rectal bleeding=0 and stool frequency ≤ 1 and PGA=0) and with mucosal healing (endoscopy score)=0 or 1, and are eligible to continue into the Double-blind Maintenance Phase.

^e This will be the final visit for subjects not entering the Open-label Acute Phase or the Double-blind Maintenance Phase.

^f The Baseline Visit (Visit 2) does not need to be repeated for subjects entering the Double-blind Maintenance Phase at the end of the Double-blind Acute Phase. Visit 3.2 will be considered the Week 0 visit for the next phase into which subjects are continuing.

^g Follow-up assessment in this phase applies only to subjects who are discontinuing the study; may be performed via telephone call within 7 days of the last dose of investigational product.

^h A visit window of ± 3 days is permitted for all study visits except for the Screening Visit (Visit 1) and the Baseline Visit (Visit 2), which must occur 3 to 21 days following the Screening Visit (Visit 1). If the initial endoscopy is not adequate for mucosal healing score assignment due to inadequate bowel preparation, to allow for a repeat endoscopy to be conducted, the period of the Screening Visit (Visit 1) can be extended by an additional 14 days from the date of the initial endoscopy.

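### The acute-phase clinical-and-endoscopic endpoint drops certain failures who complete Week 8 unscoped but keeps those who switch earlier, so the rate depends on switch timing and endoscopy uptake

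*SAP*

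**What the plan says.** The endpoint in SAP 5.8.2.1 is conjunctive. It needs a full UC-DAI of at most 2, rectal bleeding 0, stool frequency at most 1, PGA 0, an endoscopy score of at most 1, and at least a 1-point fall in that score. Two missing-data rules apply to it:

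- Missing Week 8 data count as no response.
- "Subjects who completed week 8 but who did not have central reading endoscopies at both baseline and week 8 will be excluded". The local-reading bullet repeats this: "Subjects who completed week 8 but who did not have local reading endoscopies at both baseline and week 8 will be excluded".

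Neither exclusion depends on clinical status.

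The protocol decides who is scoped. Under Protocol 7.1.2.3, endoscopy "should be performed at Visit 3.2 for subjects who are not entering into the Open-label Acute Phase", and a subject not scoped may remain in the study. Protocol 7.2.1.2 plans the full score at "Week 8 of the Double-blind Acute Phase (Withdrawal) for subjects not entering into the Open-label Acute Phase", and SAP 4.2.1 repeats this. Protocol 7.1.3 says who goes open-label at Week 8: "Subjects may enter the Open-label Acute Phase after completion of the Double-blind Acute Phase if they do not meet the requirements". The requirements meant are those of the maintenance phase.

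Switching is also allowed from Visit 3, after at least 2 weeks (Protocol 7.1.3; SAP section 11, Table 5 footnote b). Protocol 7.1.1.4 says of those who leave the double-blind phase early: "Visit 3.1 and/or Visit 3.2 may not be completed in the case that a subject enters into the Open-label Acute Phase without completing". SAP 5.8 keeps Week 8 apart from an early withdrawal visit when it defines the final on-treatment assessment: "data from the Double-blind Acute phase Week 8, or early withdrawal visit if subject withdrew prior to Week 8".

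SAP 5.8.2 and the title of Table 14.2.2.1.1 give the Double-blind Acute Phase Safety Analysis Set as the population. Protocol 9.8.3.1 has no such exclusion, nor has the matching maintenance endpoint in SAP 5.8.2.2. SAP section 6 does not list it as a change.

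**The concern.** Nothing is missing for a subject who fails a clinical component at Week 8: the composite outcome is known to be a failure. The rule still removes that subject if unscoped, and the endoscopy schedule makes this systematic, because Week 8 non-responders are the ones who may enter open-label treatment. A subject with the same lack of response who switches at Week 2 or Week 4 did not complete Week 8, so the exclusion does not apply and the subject counts as a failure. The date of a switch made on the investigator's judgement therefore decides whether a certain failure is counted.

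The reported rate is neither a Safety Analysis Set rate nor an endoscopy-evaluable rate, since unscoped early leavers remain in it. This is an estimation study, so the rates and the dose difference are what it delivers.

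**Working it through.** **Inputs from the documents.** The acute-phase sample is 53 subjects (SAP 3.5), allocated 1:1. The only uptake figure is an aim of about 30% of subjects over both acute phases combined (Protocol 7.2.1.2). No response, healing, early-switch or responder-uptake rate is given, so there is no planned figure to reproduce.

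**A direct count.** Take an assumed arm of 26 with 10 clinical responders, 6 of them scoped and 4 healed, and 16 non-responders, none scoped at Week 8. The SAP rate is 4/(6 + early switchers):

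| Early switchers among the 16 | SAP rate |
|---|---|
| 0 | 4/6 = 66.7% |
| 4 | 4/10 = 40.0% |
| 8 | 4/14 = 28.6% |
| 12 | 4/18 = 22.2% |
| 16 | 4/22 = 18.2% |

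The clinical and endoscopic results are the same in every row.

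**General formula.** Let R be clinical response, h healing among responders, s the share of responders scoped, e the share of non-responders leaving before Week 8, and q the share of Week 8 non-responders scoped.

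- True rate = R·h.
- SAP rate = R·s·h / [R·s + (1−R)·e + (1−R)·(1−e)·q].
- The two are equal when s = e + (1−e)·q, that is, when responders and non-responders are retained equally.

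**Rate.** Assume R = 0.35, h = 0.70, s = 0.5, q = 0. The true rate is 24.5% and the SAP rate is 0.1225/(0.175 + 0.65e):

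| e | SAP rate | Known failures excluded, of 53 |
|---|---|---|
| 0.1 | 0.1225/0.240 = 51.0% | 53 × 0.65 × 0.9 ≈ 31 |
| 0.3 | 0.1225/0.370 = 33.1% | 53 × 0.65 × 0.7 ≈ 24 |
| 0.6 | 0.1225/0.565 = 21.7% | 53 × 0.65 × 0.4 ≈ 14 |

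In each row about 53 × 0.35 × 0.5 ≈ 9 unscoped responders are excluded as well. At s = 0.3 and e = 0.3 the rule gives 0.0735/0.300 = 24.5%, with no bias. Over s from 0.3 to 1.0 and e from 0.1 to 0.6, the reported rate runs from 15% to 59%. With q = 0.2 it runs from 13% to 46%.

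**Dose difference.** Assume R = 0.30 vs 0.50 with equal healing, a true difference of 14 points. With q = 0 the rule reports, in points:

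| s | e = 0.1 | e = 0.3 | e = 0.6 |
|---|---|---|---|
| 0.3 | 13.1 | 14.0 | 11.0 |
| 0.5 | 10.6 | 14.6 | 13.4 |
| 0.8 | 8.0 | 13.6 | 14.5 |
| 1.0 | 6.9 | 12.7 | 14.6 |

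With q = 0.2 the range is 10.3 to 14.6.

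**False difference.** Assume R = 0.35 in both arms and s = 0.5. Early switching of 40% vs 20% gives 0.1225/0.435 = 28.2% vs 0.1225/0.305 = 40.2%, a false 12 points (6 with q = 0.2). Early switching of 35% vs 25% gives 30.4% vs 36.3%, about 6 points (3 with q = 0.2).

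**The case against.** **The magnitudes are assumed.** This is correct. No input rate is in the documents, and the 51% case sets scoping of Week 8 non-responders to zero. Open-label entry is optional, Protocol 7.2.1.2 asks for all efforts at end of phase or withdrawal, and routine-care endoscopies are collected. At 20% scoping the distortion shrinks. The false 12 points also needs twofold different early switching between blinded arms.

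**Early switchers may have Week 8 data.** Visit 3.2 is a combined Week 8/Withdrawal visit, and the open-label dose uses the weight taken there. If withdrawal data were mapped to Week 8, the subject still would not have completed Week 8, so the exclusion would not apply. A clinical non-responder would still count as a failure.

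**The set label is only a convention.** The complete-case table (14.2.1.2.4) carries the same label although early withdrawals are excluded. This weakens the label as evidence, but it does not explain discarding known outcomes.

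**The SAP may define missing-data handling.** Protocol 9.4 allows that, so the rule can be read as an elaboration.

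**Maintenance entry.** Table 1 footnote d also asks for an endoscopy score of 0 or 1. A clinical responder sent open-label on that ground has been scoped and stays in, so the point is unchanged.

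**Counting all unscoped subjects as failures can be worse for the dose comparison.** This stands. In the q = 0 grid the SAP rule is closer to the true 14 points in 8 of 12 cells, including all six at 30% and 50% uptake. With q = 0.2 it is closer in all nine cells below 100% uptake. The all-fail figure must therefore not serve as the point estimate.

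**Mitigation.** Clinical response is reported on the full set (SAP 5.8.1.1), components are summarised by arm, and p-values are descriptive.

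**Conclusion.** The concern holds as stated. The plan treats subjects with the same certain non-response in opposite ways according to when they switched, and this follows from the text without any assumed rate.

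The size and direction of bias in the rate are unknown. On the assumed inputs a true 24.5% is reported as anything from 15% to 59%, or 13% to 46% if 20% of Week 8 non-responders are scoped, and some combinations give no bias. The dose difference is distorted only if the arms differ in response, switching, uptake or healing.

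This should be fixed, but it is limited to a descriptive secondary endpoint (central and local versions).

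**What to change.** Delete the exclusion sentence in both bullets and keep the Safety Analysis Set as denominator.

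1. Count any subject who fails a clinical component at Week 8, or has no Week 8 assessment, as a non-responder, scoped or not.
2. Treat only Week 8 clinical responders without paired endoscopies as unknown. Report their number by arm, with all-fail and all-success bounds for the rate and the dose difference.
3. If the planned continuity-corrected chi-squared or Fisher test is run on the all-fail version, label that version the lower bound for the rate. State that low uptake understates the rate and shrinks the dose difference.
4. Show clinical response × healing (with the 1-point reduction) among scoped responders only as a supportive estimate under missing at random. Use an interval that works at 0% or 100% observed healing, for example quantiles of the product of independent Beta(x+0.5, n−x+0.5) draws. Omit it for an arm with no scoped responder.
5. Record the change in SAP section 6, which already covers sparse endoscopy data for the maintenance endpoints.

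**Cost.** SAP wording and a few lines of programming, with no new data. On the same assumed inputs, with all-fail = R·s·h and all-success = R·s·h + R·(1−s):

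| | 30% uptake | 50% uptake |
|---|---|---|
| Bounds for the true 24.5% | 7–32% | 12–30% |
| Bounds for the true 14 points, arms treated alike | 4.2–18.2 | 7.0–17.0 |
| Bounds for the true 14 points, extremes | −16.8 to 39.2 | −8.0 to 32.0 |
| Observed healing 0%, 100% or undefined, per arm of 26 | 52% | 27% |

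In that arm of 26, a delta-method 95% interval for the product covers about 84% (30% uptake) or 90% (50%). The Beta-draw interval covers about 94%, with a half-width of 17 to 18 points.

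In return, the direction of error of the all-fail rate is known and switch timing no longer matters: early switching of 40% vs 20% gives 0 instead of a false 12 points. Unequal uptake still matters. Uptake of 30% vs 50% gives a false 4.9 points, against 8.6 under the SAP rule with 30% early leaving.

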5.8.2 Secondary Efficacy Endpoints and Analysis

The secondary endpoints for this study are defined separately for both the Double-blind Acute and Double-blind Maintenance Phases and will be conducted using the appropriate Safety Analysis Set for the phase.

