5.8.2.2 Double-blind Maintenance Phase

- The proportion of subjects who have maintained a clinical and endoscopic response at Week 26, defined as UC-DAI ≤ 2 with rectal bleeding=0 and stool frequency ≤ 1 and PGA=0 and with mucosal healing (endoscopy score ≤ 1) based on central reading. This endpoint will be compared between treatment arms using a CMH test stratifying by Week 8 responder status. Subjects with missing data at Week 26 will be assumed not to have had a clinical response. If there are an insufficient number of subjects with central reading endoscopy data, then the CMH test will not be performed. The number and percentage of subjects with clinical and endoscopic response – based on central response will be presented by treatment arm.
- The proportion of subjects who have maintained a clinical and endoscopic response at Week 26, defined as UC-DAI ≤ 2 with rectal bleeding=0 and stool frequency ≤ 1 and PGA=0, and with mucosal healing (endoscopy score ≤ 1) based on local reading. This endpoint will be compared between treatment arms using a CMH test stratifying by Week 8 responder status. Subjects with missing data at Week 26 will be assumed not to have had a clinical response. If there are an insufficient number of subjects with central reading endoscopy data, then the CMH test will not be performed. The number and percentage of subjects with clinical and endoscopic response – based on local response will be presented by treatment arm.
- The change in the DUCS score from Double-blind Maintenance Phase Week 0 to Week 26. This endpoint will be compared between treatment arms using an analysis of covariance, including treatment arm as a factor, the DUCS score at Double-blind Maintenance Phase Week 0 and Week 8 responder status as covariates in the model.
- The percentage of subjects in remission (PUCAI < 10) at Double-blind Maintenance Phase Week 26. This endpoint will be compared between treatment arms using a CMH test stratifying by Week 8 responder status. Subjects with missing data at Week 26 will be assumed not to have had a clinical response.

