7.2 Handling of Dropouts or Missing Data

For the primary analysis of the primary efficacy endpoint, subjects with missing data at Week 8 or Week 26 for the Double-blind Acute Phase or Double-blind Maintenance Phase, respectively, will be assumed not to have had a clinical response and will be considered treatment failures.

Sensitivity analyses to examine the handling of missing data for the primary efficacy endpoint include complete-case analysis and last observation carried forward. These are described in Section 7.7.

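### The DUCS change endpoints have no missing-data rule; if children without a Week 8 or Week 26 value are dropped, selective exits can pull the dose comparison toward no difference

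*SAP*

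**What the plan says.** SAP 5.8.2.1 defines the acute endpoint as "The change in the DUCS score from baseline to Week 8 of the Double-blind Acute Phase" and compares the doses by ANCOVA, "including treatment arm as a factor and the baseline DUCS score as a covariate in the model". SAP 5.8.2.2 does the same for "The change in the DUCS score from Double-blind Maintenance Phase Week 0 to Week 26", adding Week 8 responder status. Neither entry says what happens when the end-of-phase value is missing.

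The other secondary endpoints are treated differently. In SAP 5.8.2.1 each of the three binary endpoints carries the rule "Subjects with missing data at Week 8 will be assumed not to have had a clinical response", and SAP 5.8.2.2 has the matching Week 26 rule. SAP 7.2 opens with "For the primary analysis of the primary efficacy endpoint, subjects with missing data at Week 8 or Week 26" and says nothing about DUCS. The complete-case and LOCF analyses in SAP 7.7.1 are for the primary endpoint only. SAP 8.2 contains no DUCS derivation.

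On exits, Protocol 7.1.3 lets children enter the Open-label Acute Phase "provided they have participated in the Double-blind Acute Phase for a minimum of 2 weeks" and, in the investigator's view, "have not benefited from treatment in the Double-blind Acute Phase". Protocol 7.1.1.4 notes that Visit 3.2 may be absent for a child who moves early. Protocol 4.5 and 7.1.2.3, with Table 1, provide for a withdrawal visit that includes the DUCS diary.

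**The concern.** An ANCOVA on one visit, run as written, drops any child without that visit's value. In the acute phase one permitted reason for leaving blinded treatment early is lack of benefit, so the children lost may be those doing worst. If the low dose works less well, more low-dose children leave, the remaining low-dose children look better than the arm as a whole, and the estimated dose difference shrinks.

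The plan describes itself as an estimation study (SAP 5.1), so a biased estimate matters even though p-values are only descriptive. DUCS is also collected before Weeks 2 and 4 in the acute phase and before Week 13 in Maintenance (Protocol Tables 1 and 3), and the planned ANCOVA uses none of these values.

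**Working it through.** **No plan figure to reproduce.** The documents give no DUCS effect, SD, correlation or exit rate, and no power calculation. All such inputs below are assumptions.

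**Model under check.** Change at Week 8 = intercept + dose effect × arm + slope × baseline, fitted to children with a Week 8 value.

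**Assumptions.** DUCS in SD units, with lower taken as better. True high-minus-low difference at Week 8 of −0.50, of which 40% (−0.20) is present at Week 2 and 70% (−0.35) at Week 4. Correlation between adjacent post-baseline visits 0.6 or 0.75; baseline with Week 8, 0.4. A child exits at Week 2 or Week 4 when observed change plus random noise (SD 0.5) is worse than a cut-off common to both arms, set to give total exits of 10% to 40%. 400,000 simulated children per setting.

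**Exits related to DUCS** (full = all children kept on randomised dose):

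| Exits | Kept, low/high | Corr. 0.6: full → completers | Ratio | Corr. 0.75: full → completers | Ratio |
|---|---|---|---|---|---|
| 10% | 88/92% | −0.502 → −0.472 | 94% | −0.501 → −0.462 | 92% |
| 20% | 76/84% | −0.500 → −0.454 | 91% | −0.500 → −0.438 | 88% |
| 30% | 65/75% | −0.497 → −0.435 | 88% | −0.498 → −0.419 | 84% |
| 40% | 54–55/65% | −0.501 → −0.435 | 87% | −0.494 → −0.392 | 79% |

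As an example of the ratio, 0.392 / 0.494 = 0.79. A second set of assumptions gave 81% to 90%: true difference 0.4 to 0.6 SD, a fixed Week 4 cut-off, and exits of 20% to 40% on low dose and 10% to 30% on high dose.

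**Exits unrelated to DUCS.** Completers gave 99% to 101% of the full-data estimate, both with equal exits and with more exits on high dose.

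**No true dose difference.** A common exit rule then removes the same kind of child from both arms, and the completer estimate is unbiased.

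**Alternatives on the same simulated data.**
- Predicting Week 8 from Weeks 2 and 4 (missing at random) gave −0.49 to −0.50 under DUCS-related exits.
- Carrying the last on-treatment value forward gave −0.48 to −0.53 under DUCS-related exits. With unrelated exits it gave −0.41 to −0.48 (equal arms) and −0.16 to −0.41 (more exits on high dose). LOCF is therefore not a safe single remedy.

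**Scale against precision.** SAP 3.5 gives N = 53, so 27/26. With baseline correlation 0.4, SE = √(1 − 0.4²) × √(1/27 + 1/26) = 0.917 × 0.275 = 0.25 SD. The bias runs from 0.502 − 0.472 = 0.03 to 0.494 − 0.392 = 0.10 SD, which is under half a standard error. Separately, the mean number analysed falls from 53 to about 48, 42, 37 and 32 at exits of 10%, 20%, 30% and 40%.

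**The case against.** A reader might infer that the plan uses only children who reach Week 8. No passage says so. Secondary analyses are "conducted using the appropriate Safety Analysis Set for the phase", Visit 3.2 doubles as a withdrawal visit, and a child who switches early may well have DUCS from it. On the other side, Protocol 7.1.1.4 allows that visit to be missing, and SAP 5.8 lists Week 8 and early withdrawal as distinct sources in its final on-treatment assessment, while the DUCS endpoint names Week 8. What stands is that the plan leaves open whether withdrawal-visit DUCS counts. A separate DUCS SAP exists (SAP 4.3.1) and was not available; Protocol 9.10.1 describes it as covering validation. If it holds a rule, this SAP needs a cross-reference.

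It is also tempting to say that the comparison is diluted, and equally so in both phases. Dilution needs a real dose effect and DUCS-related exits. The Week 2 transfer route exists only in the acute phase. In Maintenance, loss would come from withdrawal, for example for lack of efficacy (Protocol 4.5.1), and no calculation was made for it.

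A third tempting reading is that a repeated-measures model restores the full difference. In the simulations that recovery is built in, because exits depended on observed DUCS plus noise. The protocol's trigger is the investigator's opinion, which may draw on information outside DUCS.

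Finally, this is a secondary endpoint in a study not powered for dose differences, and the bias is small beside the sampling error. That limits the priority but does not remove the gap.

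**Conclusion.** The concern holds in a conditional form. Both DUCS change endpoints lack any missing-data rule or sensitivity analysis, and nothing elsewhere in the SAP supplies one. In the acute phase, if children without a Week 8 value are dropped, exits follow DUCS and the doses differ, completers recover about 79% to 94% of the true difference for assumed exit rates of 10% to 40%. Outside those conditions there is no bias. The percentages rest on assumed effects, correlations and exit rates, and on a target of remaining on the randomised dose. In Maintenance the gap in the text is the same, but the mechanism is selective withdrawal and its size is unknown. The change is worth making before unblinding, but it does not threaten the primary endpoints.

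**What to change.** **SAP 5.8.2.1.** Make the main analysis a mixed model for repeated measures on DUCS change at Weeks 2, 4 and 8, with arm, visit, arm-by-visit, baseline DUCS and baseline-by-visit. Use data up to the last blinded dose and report the Week 8 contrast. State that this estimates the effect had children stayed on blinded treatment, which differs from the primary endpoint's strategy of counting missing outcomes as failures. State how withdrawal-visit DUCS is assigned to a model visit.

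**SAP 5.8.2.2.** Use the same approach with Weeks 13 and 26, keeping Week 8 responder status. The mapping of withdrawal-visit DUCS matters more here: a child who leaves before Week 13 otherwise contributes no scheduled outcome.

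**Both phases.** Keep the completer ANCOVA as a sensitivity analysis, add one missing-not-at-random sensitivity analysis, and report the number of missing DUCS values by arm and reason.

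**Protocol.** Sections 7.1.1.4, 4.5 and 7.1.2.3 must be reconciled on whether a child who moves early has a Visit 3.2.

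**Cost.** SAP wording, one model per phase and a little more analysis work; no new data. The main estimate will rely on missing at random, which is why the missing-not-at-random analysis is needed.
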